9.2 Study design

The source cohort will consist of all individuals aged five years and older as ascertained by the date of first vaccination. The main cohort will consist of individuals aged 18 years or older. We will examine an additional cohort of individuals aged 5 to 17 years old in tertiary analyses – note that not all countries can contribute information in the 5- to 11-year olds. The cohort participants will be classified according to SARS-CoV-2 vaccinations received and followed from the 2. or 3. dose using survival analysis. For 5- to 11-year olds, only the BNT162b2 in a reduced dose has been approved for use (since 25 November 2021). We will apply different study designs according to the objective in question; see subsection *Statistical Analysis* below.

Eligibility criteria for study inclusion will be:

- having received at least the primary immunization (i.e. 1. and 2. vaccine dose against covid-19) with either AZD1222, BNT162b2 or the mRNA-1273 vaccines (for the purpose of objective #5, being vaccinated will not be an eligibility criterion),
- known residency within the specific country,
- and no positive reverse transcription polymerase chain reaction (PCR) test before the study period start and before receiving a 2. or 3. dose in the distinct schedule evaluated.

EMA has previously advised that groups of people with severely compromised immune systems should be offered a 3. dose at least 28 days after the 2. dose as part of their primary vaccine series (https://www.ema.europa.eu/en/news/comirnaty-spikevax-ema-recommendations-extra-doses-boosters). Thus, a short inter dose interval (28-days to 90-days) between the 2. and 3. dose, will be an exclusion criteria.

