The endpoints will be: 1) a positive PCR test for SARS-CoV-2 (i.e. infection), 2) a covid-19 hospitalization, 3) covid-19 hospitalization at an intensive care unit (ICU) and 4) covid-19 related death. In the primary analyses we will follow up for the endpoints from start of follow-up defined as day 14 after the index date, and until 75 days have elapsed since the start of follow-up. These outcome ascertainment periods have been chosen to balance: a) that the follow-up among the comparison groups will be homogenous in contrast to longer periods of outcome ascertainment where right censoring at study end or another dose may differ substantially between comparison groups, and b) that we need to have sufficient follow-up for the assessment of hospitalization and mortality. When evaluating waning of immunity, follow-up for endpoints will continue beyond day 75.

Covid-19 hospitalization

Covid-19 hospitalization will be defined as an event fulfilling the following criteria: a) hospitalization with a PCR positive test for SARS-CoV-2 dated in the time period beginning 14 days before admission (day -14; the day of admission is day 0) and up to and including 2 days

after admission (day 2), b) inpatient hospital contact or a hospital contact with a duration of at least 12 hours and c) a covid-19 relevant diagnosis code (ICD-10: B342, B342A, B948A, B972, B972A, B972B, B972B1 or Z038PA1 – subject to country-specific coding practices, see table below - TIME-VARYING VARIABLES). Thus, individuals who are hospitalized for conditions not related to covid-19, but who coincidentally test positive in the period around admission (14 days before to 2 days after admission) will be included as an endpoint 1 (infection) but not an endpoint 2 (hospitalization). An example of this could be a patient with a fracture who test positive at admission as part of routine testing. This distinction is particularly important to make during periods of high incidence of infection as in the period of omicron. Covid-19 hospitalization to an ICU (endpoint 3) will be assessed among those individuals fulfilling the criteria for covid-19 hospitalization (endpoint 2).

Covid-19 related mortality

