At the day an individual receives a 3. dose (i.e. the index date) of the studied schedule, the individuals will be matched with an individual having received the respective 2-dose comparison schedule (i.e. controls) but have not yet received a 3. dose (i.e. at the this date). For each matched pair, the index date of the individual in the 3-dose studied schedule will be assigned to the 2-dose comparison schedule control individual. The matched controls will be eligible to be included in a 3-dose studied schedule group in case of receiving a future 3. dose to that of the given matched date. Individuals from the 3-dose studied and the 2-dose comparison schedules will be matched on age (5-year bins), calendar month of receiving the 2. dose and a propensity score summarizing potential confounders such as sex, vaccination priority group and comorbidity. The time at which an individual was vaccinated with a 2. dose, is highly correlated with risk of severe covid-19 and/or risk behavior due to the national prioritization of the rollout of the covid-19 vaccines (e.g. individuals of high risk of severe covid-19 and health care workers were prioritized for earlier vaccination than the general public).

Individuals in the country-specific cohorts will be followed from the time they enter one of the vaccination schedules groups and 13 days have passed until one of the endpoints included in the study, end of endpoint ascertainment period, received a booster dose (a 3. dose for 2-dose schedules and a 4. dose for 3-dose schedules), exit from the cohort due to death, loss to follow-up, emigration, or end of study period, whichever occurs first. I.e. for the 3- vs. 2-dose matched comparisons, follow-up for the matched pairs will also end if the control individual receives a 3. dose (on that date; see example in Figure 4B). Follow-up will be conducted separately for each outcome without censoring for the other study outcomes. That is, when evaluating effectiveness against covid-19 hospitalization to an ICU, having a positive PCR test for SARS-CoV-2 or being covid-19 hospitalized does not right-censor the follow-up for this individual. However, note that when the 14 days and 30 days, respectively, after a positive test has passed, the follow-up will be censored in the analyses of hospitalization and ICU, and mortality, respectively.

[figure not shown]

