Risk differences (RDs) and risk ratios (RRs) will be estimated using cumulative incidences at day 75 after start of follow-up (i.e. day 14 after index date) for the 3. dose schedule being studied and the 2. dose comparator schedule, respectively in the matched populations. Comparative VE will be calculated as 1 – RR (for RR < 1.00). The propensity score for matching will be estimated as the probability of the 3. dose studied schedule conditional on covariates in the combined population of both schedules using logistic regression including direct adjustment for year of birth (5 year categories; proxy for age), sex, calendar month (monthly categories), comorbidity and vaccination priority group. We will calculate 95% CIs using the nonparametric bootstrap method with 1000 repetitions.

Meta-analyses

Where feasible, country-specific effect estimates will be combined using meta-analysis based on random-effects models implemented using *mixmeta* package of R. We will test for homogeneity of effects across countries using the Cochran Q test and will use the delta method to construct 95% CIs assuming independence. For those comparisons where metaanalysis are not feasible, we will present the country-specific results individually.

Intended additional analyses

In secondary analyses, we will stratify comparative VE estimates according to calendar periods of Alpha, Delta and Omicron variant dominance (i.e. when it is estimated that the variant of concern accounts for more than 90% of all cases) or using variant-PCR/WGS results, subject to national availability. These periods will be defined on a country-specific basis, based on the nationally surveillance data on variants of dominance.

Danish variant situation

The calendar periods for specific variant dominance in Denmark are: Alpha/Beta period, 15 March to 30 June 2021; Delta period: 15 July to 15 November 2021; and Omicron period: 28 December 2021 to 28 February 2022. The intermediary transition periods will be left out. As data availability permits, we will in addition assign each endpoint a variant using variantspecific test results or results from whole-genome sequencing (WGS). As an example, in Denmark we utilize both WGS and variant-PCR in covid-19 surveillance.

Finnish variant situation

Alpha/Beta period, 15 March to 9 May 2021; Delta period, 21 June to 27 November 2021; and Omicron period (BA.1), 1 January to 28 February 2022. The intermediary transition periods will be left out.

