As both the utilized vaccine schedules, time of vaccination, and doses differ among children and adolescents to the adult population, the vaccine effectiveness of children and adolescents will be examined in a separate cohort. Among adolescents (12- to 17-year olds), we intend to examine similar objectives as outlined for the adult population; however, these analyses will be confined to 2-dose regimens (as the countries have not yet consistently utilized a 3. [booster] dose for this younger population by the time of this study protocol). For children (5to 11-year olds), we will compare 1 or 2 doses to unvaccinated children (with a study design similar to that of the 3- vs. 2-dose comparisons in the main cohort), since only BNT162b2 has been used in this age group in the Nordic countries, precluding comparative measures. We will evaluate the following endpoints: infection, hospitalization and diagnosis of multisystem inflammatory syndrome in children (MIS-C).

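### The vaccinated vs unvaccinated comparison in 5- to 11-year-olds borrows a day-75 read-out that the two-dose arm cannot reach before study end and that only the first week of one-dose children can reach

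*Protocol*

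**What the plan says.** Protocol section 9.7, *Children and adolescents population*, sets the analysis for ages 5 to 11: "we will compare 1 or 2 doses to unvaccinated children (with a study design similar to that of the 3- vs. 2-dose comparisons". It gives no start of follow-up, horizon or censoring rule of its own.

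The design it points to is fixed elsewhere:

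- **Start and length of follow-up.** Section 9.3, *Outcomes*, has "start of follow-up defined as day 14 after the index date", running "until 75 days have elapsed since the start of follow-up".
- **Read-out.** Section 9.7, *Adjusted cumulative incidences - 3-dose vs 2-dose comparisons*, takes "cumulative incidences at day 75 after start of follow-up (i.e. day 14 after index date) for the 3. dose schedule being studied" and for its comparator.
- **Next-dose censoring.** Section 9.7 ends follow-up when a person has "received a booster dose (a 3. dose for 2-dose schedules and a 4. dose for 3-dose schedules"). Dose 2 is not named. In addition, "follow-up for the matched pairs will also end if the control individual receives a 3. dose".
- **Calendar limits.** Section 9.2 says that in this age group "only the BNT162b2 in a reduced dose has been approved for use (since 25 November 2021"). Section 9.1 ends the study on 28 February 2022.

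Section 9.5 describes the paediatric schedule as two doses. The interval between them is not stated anywhere in the protocol.

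**The concern.** The borrowed design was built for adults followed from a booster dose. Two of its features do not carry over to young children.

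First, the child programme began shortly before study end, so a window ending 89 days after the index dose may not fit in the calendar. A curve with nobody under observation at day 75 gives no day-75 risk. Carrying its last value forward would report the risk at an earlier day under the wrong label.

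Second, a one-dose arm in a two-dose schedule is transient, and the censoring rule does not say what happens at dose 2. The part of objective 5 that concerns 5- to 11-year-olds could therefore report a two-dose effectiveness that was not observed, and a one-dose effectiveness whose later part comes from an unrepresentative remainder.

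**Working it through.** The protocol gives no sample size or event figure for this comparison, so there is none to reproduce. The check is day arithmetic.

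**Inputs**

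- Start of follow-up: day 14 after the index dose (9.3).
- Read-out: 75 days later (9.3, 9.7), so day 14 + 75 = 89 after the index dose.
- Earliest child vaccination: 25 November 2021 (9.2).
- Study end: 28 February 2022 (9.1).
- Interval between doses 1 and 2: *d* days. It is not in the protocol, so I varied it over 3, 4, 6, 8 and 12 weeks as an assumption.
- Index date of the one-dose arm: taken as dose 1. This is also an assumption, because section 9.3 defines the index date only for a second or third dose.

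**Calendar time available**

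25 November 2021 to 28 February 2022 is 5 + 31 + 31 + 28 = 95 days. After the 14-day lag, 95 − 14 = 81 days remain for a child vaccinated on the first possible day.

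**Two-dose arm**

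Dose 2 falls *d* days after dose 1, so the longest follow-up after its own day 14 is 81 − *d*. Reaching day 75 requires 81 − *d* ≥ 75, that is *d* ≤ 6 days.

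**One-dose arm**

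The last dose-1 date that allows a full window is 28 February 2022 − 89 days = 1 December 2021. Only children given dose 1 from 25 November to 1 December 2021 can be observed at day 75, whatever is done at dose 2.

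If follow-up ends at dose 2, a child who takes it after *d* days contributes *d* − 14 one-dose days. Beyond that point the curve rests on children who delayed or skipped dose 2.

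| Assumed interval *d* | Longest two-dose follow-up, 81 − *d* | One-dose days if censored at dose 2, *d* − 14 |
|---|---|---|
| 21 days | 60 | 7 |
| 28 days | 53 | 14 |
| 42 days | 39 | 28 |
| 56 days | 25 | 42 |
| 84 days | none (−3) | 70 |

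No row reaches 75 in either column. The two-dose figures are upper limits: they apply to a child vaccinated on the first day, and a pair may end earlier if the control is vaccinated.

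**The case against.** **Day 75 may not be binding here.** Section 9.3 sets the window for the primary analyses, objective 5 is tertiary, and a similar design need not be an identical one. Section 8 also limits objectives 3 to 5 to schedules with sufficient information and mentions the end of the study period. Horizon details for one subgroup could sit in an analysis plan that is not shown.

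This has some weight, but it does not remove the point. Section 9.8 uses almost the same phrase for adults with two doses vs unvaccinated, and there it spells out a day-14 start and day-75 cumulative incidences. It also names its one departure in matching; the child section names none. The only exception to the window in section 9.3 is waning, which runs longer. The clause in section 8 decides whether a schedule is evaluated, not at which day. Applied with day 75 kept, it would simply remove the two-dose analysis.

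**A stronger reading is tempting but not supported.** A reader might infer that one-dose children are never censored at dose 2, so that the one-dose estimate is mostly two-dose time. The protocol does not say this. Its rule ends follow-up at the next dose, and it names doses 3 and 4 because the main cohort has only two- and three-dose schedules. Section 9.8 likewise censors vaccinated persons at their next dose, and section 9.3 treats vaccination status as time-varying, with single-dose levels. Ending at dose 2 is the more natural reading.

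Even on the literal reading, two-dose time exceeds half of a full window only if the interval is below 14 + 75/2 = 51.5 days, and no interval is given. At 8 weeks the share is 33/75 = 44%.

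**Two further limits stand.** The text could also mean a pooled group with at least one dose, for which follow-up through dose 2 would be intended. And under dose-2 censoring every child informs the curve up to dose 2; only the later part is selective. Dose 2 postponed because of documented infection is not a good example of that selection. A positive test is itself the infection endpoint, and hospitalization follow-up is censored once 14 days have passed after it.

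**Conclusion.** The point holds in this form: the child section adopts the day-14 to day-89 window without adapting it to a programme that had 95 days to run.

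- **Two doses.** The day-75 risk cannot be observed for any dose interval above 6 days. This needs no assumed interval, only the two calendar dates and the borrowed window. At assumed intervals of 3 to 8 weeks, the longest possible follow-up is 60 down to 25 days.
- **One dose.** Day 75 is observable only for children vaccinated in the first week after approval. If dose 2 ends follow-up, as is natural but not written, risk beyond (interval minus 14) days comes from children who delayed or skipped it. How much this matters depends on the unstated interval: little at 12 weeks, a great deal at 3 or 4.

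The documents do not establish that censoring at dose 2 is absent, nor that the one-dose estimate is mostly two-dose time. The effect is confined to the 5- to 11-year-old part of a tertiary objective. It is still more than a missing detail, because the design fixed by reference conflicts with the protocol's own dates.

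**What to change.** Amend section 9.7, *Children and adolescents population*, as follows.

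1. **Define the one-dose arm.** Either state that the index date is dose 1, that follow-up of the pair ends when the vaccinated child receives dose 2, and that risk is read at a horizon within the dose interval observed in that country. Or, if at least one dose is meant, label it so and follow through dose 2.
2. **Replace day 75 for the two-dose estimate, and for any at-least-one-dose estimate.** Use the longest day that calendar time and numbers at risk support in each country, chosen from vaccination dates and without reference to outcomes. A single fixed day should not be written in before the intervals are known: even day 30 would be out of reach at an 8-week interval, where the maximum is 25 days.
3. **Pooling.** If country estimates are combined, use a day that all contributing countries can support.

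The cost is protocol wording and re-set horizons, with no new data. The downside is that effectiveness in young children will cover a shorter period than in adults, and the report must say so when the two are set side by side.

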9.8 Supplementary analyses and quality control

Quality control will be conducted indirectly to evaluate the validity of our main analyses, by making sure that 1) the prevalences of the different schedules and the number of study endpoints match national surveillance dashboards and reports, 2) conduct comparisons between 2-dose schedules and unvaccinated for all study endpoints, to make sure that we are able to recover VE estimates compatible with the current evidence, and 3) utilize a test-negative study design for selected main comparisons.

We will ensure the scientific quality of the work, by division of review tasks (including statistical code review) and responsibilities in a timely fashion and by adhering to the ENCePP Code of Conduct (see attachment).

Quality control analysis: 2-dose vaccine schedules vs. unvaccinated

Individuals having received homologous primary (2-dose) vaccine schedules of BNT162b2 and mRNA-1273 (i.e. the two most common schedules) will be compared with unvaccinated individuals (controls) with a study design similar to that for objective 2 (i.e. the 3- vs. 2-dose comparison) and as previously done.(47) In these sensitivity analyses, we will evaluate the infection endpoint (positive PCR test for SARS-CoV-2). Vaccinated individuals will be matched 1-to-1 (same matching variables as the main design [except, this analysis will not include calendar month of receiving the 2. dose as not applicable] – age, sex, comorbidity and vaccination priority group) with individuals that were unvaccinated at the vaccinee's day of vaccination. Follow-up will start on day 14 after the 2. vaccine dose (for both the vaccinated and unvaccinated controls [i.e. unvaccinated controls will be assigned the index date of the vaccinated matched individual]) and end at: the day of testing positive, exit from the cohort due to death, loss to follow-up, emigration, vaccination of the matched unvaccinated control or

receipt of a (third) booster dose for vaccinated persons, or end of study period, whichever occurs first. Individuals that will be included as unvaccinated controls will also be eligible to enter the study as vaccinated. Survival curves for vaccinated and unvaccinated-control groups will be estimated using the Kaplan-Meier estimator yielding cumulative incidences at day 75 after start of follow-up. We will calculate 95% confidence intervals using the percentile bootstrap method with 1000 repetitions.

Quality control analysis: 3- vs. 2-dose schedule comparisons using a test-negative case-control study design

As an additional quality control, we will apply a test-negative case-control study design as previously done(19,21) to estimate VE against infection (positive PCR test SARS-CoV-2) in 3-vs 2-dose schedule comparisons. The results of these analyses will be compared to the corresponding comparison results from our main analysis. This will inform us on the possible impact of selection bias arising from differences in who is being tested.

Data on all (positive or negative) test results for the period 27 December 2020 to 28 February 2022 will be extracted for those aged 18 years or older (as of 27 December 2020). We will exclude any negative PCR test results taken within 3 days of a previous negative test result (as these results likely represent the same episode), negative test results taken within 21 days before a positive test result (as these are likely to be false negative), and positive and negative test results within 90 days of a previous positive test result. Since we will be evaluating the effectiveness of a 3. dose, only PCR tests taken from the date where the booster doses rollout started, specific for each country (i.e. in Denmark: 6 September 2021 [week 37, 2021]), will be retained for analysis. Participants will contribute with only one randomly chosen negative test result in the follow-up period. The 3. (booster) doses will be identified after this date and there must be at least 6 months (from 6 September 2021 to 13 December 2021 - subject for country-specific variation) or 4.5 months (from 14 December 2021 to 28 February 2022) between the 2. and 3. dose or from 2. dose and onset (i.e. of covid-19 related event). These time periods of "since 2. dose" denotes whether an individuals is eligible of receiving a 3. dose as per national-specific health authority guidelines on booster vaccination rollout. The effectiveness of a 3. dose from day 14 to day 28 (after the index date) will be compared with 2. dose schedules with onsets of events after at least the abovementioned 6 or 4.5 months eligibility criterion as well as to the immediate short period after the booster dose (i.e. the first 2-6 days; day 0 and 1 will not be included due to the potential risk of bias related to any testing due to initial reactogenicity).

VE (1 – the odds of vaccination in cases divided by the odds of vaccination in controls) will be estimated using logistic regression (the PCR test result as the dependent variable); cases will

be those testing positive and controls will be those testing negative. The logistic regression models will be adjusted for age, sex, calendar month, vaccine priority group and comorbidity similar to the main analysis.

Please note that country participation for this sensitivity analysis will likewise be subject to the usability of each national booster vaccination rollout strategies to implement this design as well as the availability of dates of negative tests.

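### The test-negative check covers days 14-28 after dose 3 but is compared with a 75-day main estimate, so a difference or an agreement cannot by itself inform on testing-related selection

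*Protocol*

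**What the plan says.** **Main 3- versus 2-dose analysis.** Section 9.3 (Outcomes) sets the primary follow-up as "defined as day 14 after the index date, and until 75 days have elapsed since the start of follow-up", so roughly days 14 to 89 after dose 3. Section 9.7 estimates effectiveness as one minus the risk ratio, "using cumulative incidences at day 75 after start of follow-up (i.e. day 14 after index date) for the 3. dose schedule being studied".

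**Test-negative quality control.** Section 9.8 restricts the exposed window: "The effectiveness of a 3. dose from day 14 to day 28 (after the index date) will be compared with 2. dose schedules". The same sentence adds a second comparator, days 2-6 after the booster. The measure is an odds ratio: "VE (1 – the odds of vaccination in cases divided by the odds of vaccination in controls) will be estimated using logistic regression". Of the planned comparison with the main result, the section says: "This will inform us on the possible impact of selection bias arising from differences in who is being tested". No other reason for a difference is named.

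**No bridging estimate.** Section 9.7 fixes day 75 as the only horizon for 3 versus 2 doses. Its waning analyses compare schedules only for 2 versus 2 and 3 versus 3 doses, from day 120 on. Within-schedule waning is judged against day 75.

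**The other quality control.** The opening list of section 9.8 says the team will "conduct comparisons between 2-dose schedules and unvaccinated for all study endpoints". The detailed subsection then says: "In these sensitivity analyses, we will evaluate the infection endpoint (positive PCR test for SARS-CoV-2".

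**The concern.** For the comparison to say something about who is tested, the two analyses should estimate the same effect and differ mainly in how testing enters. Here they cover different stretches of time since dose 3. The test-negative window is the first fifth of the main window, when protection should be highest. Section 7 of the protocol says that protection against infection is lost quickly.

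PCR positivity is the primary outcome, and section 9.9 concedes that only people who test positive are captured. This comparison is the one the protocol names as informing on testing-related selection. If the windows differ, a lower main estimate may be waning alone. If the results agree, a testing bias may have been cancelled by waning, which would be false reassurance.

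**Working it through.** The protocol gives no figure for this analysis, so there is none to reproduce. The check compares the rules and then illustrates the size.

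**1. Windows.** Main: day 14 to day 14 + 75 = 89. Test-negative: days 14-28, which is 28 − 14 + 1 = 15 days inclusive; 15/75 = 20% of the main window.

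**2. Effect of the window alone.** Assume no testing bias, constant risk over time, effectiveness of 55% up to day 28, then a linear fall to v at day 89. The starting value is of the order of the 54.6% that section 7 cites for a third dose; the values of v are assumed. The first segment is 28 − 14 = 14 days and the second 89 − 28 = 61 days:

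average = [14 × 55 + 61 × (55 + v)/2] / 75

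| v at day 89 | Average, days 14-89 | Gap from 55% |
|---|---|---|
| 45% | 3820/75 = 50.9% | 4.1 points |
| 35% | 3515/75 = 46.9% | 8.1 points |
| 25% | 3210/75 = 42.8% | 12.2 points |
| 15% | 2905/75 = 38.7% | 16.3 points |

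**3. Second model, using the protocol's own measure.** Let effectiveness fall linearly from 54.6% at day 14 to v at day 89, with constant hazard in the 2-dose group and 75-day risk R2 (assumed 5%, 20% or 40%). Then:

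- mean effectiveness m = (54.6% + v)/2
- 3-dose risk R3 = 1 − (1 − R2)^(1 − m)
- main estimate = 1 − R3/R2
- test-negative estimate, taken as the mean effectiveness over the first 15 days = 54.6% − (54.6% − v) × 7.5/75

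Example: v = 25%, R2 = 20%. m = 39.8%; R3 = 1 − 0.8^0.602 = 12.57%; main = 37.1%; test-negative = 51.6%; gap 14.5 points.

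| v at day 89 | Gap, R2 = 5% | R2 = 20% | R2 = 40% |
|---|---|---|---|
| 54.6% (no waning) | 0.6 | 2.8 | 6.3 |
| 40% | 6.5 | 8.6 | 12.1 |
| 25% | 12.5 | 14.5 | 17.8 |
| 0% | 22.3 | 24.0 | 26.7 |

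The first row is the effect measure alone: a cumulative risk ratio drifts toward 1 as risk accumulates.

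**4. What an early benchmark does.** Reading the cohort over the same 15 days gives a 2-dose risk of 1 − (1 − R2)^(15/75), that is 1.0%, 4.4% or 9.7%. Applying the same formula to these 15 days, the gap falls to 0.1, 0.6 or 1.3 points, whichever waning path is assumed. Matching the window removes the waning component and most of the effect-measure component.

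**The case against.** **The plan's wording is modest.** It says the comparison will inform on a possible impact. A reader might infer that the plan attributes any disagreement to testing; it does not say that. Still, selection is the only explanation it offers, and no estimate is planned that would separate it from waning.

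**There is a second comparator.** The days 2-6 contrast is made within boosted people, does not depend on the main analysis, and bears on selection between boosted and unboosted people. So it would be too strong to say the protocol has no other handle on the problem. That contrast also uses days 14-28, however, so it does not close the gap with the 75-day result.

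**Prior infection.** The test-negative filters remove "positive and negative test results within 90 days of a previous positive test result", and a reader might infer that people infected earlier stay in, unlike in the main cohort. The text does not establish this. The section 9.2 criterion of no earlier positive test is written for the whole study, section 9.8 does not lift it, and the 90-day filter reads naturally as cleaning of repeat tests. What stands is that section 9.8 leaves the matter unclear.

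**Dose interval.** The test-negative analysis requires 6 or 4.5 months since dose 2; the main analysis only excludes intervals of 28 to 90 days. A reader might infer that the test-negative rule should be relaxed to match. The documents do not support that. The protocol ties the rule to national booster eligibility, the analysis is unmatched, and its listed covariates do not include month of dose 2. Relaxing it could admit people with two doses who are not comparable. The effect of the difference cannot be computed from the protocol and may be small.

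**The size is assumed.** This is correct. The protocol gives no waning curve for 3 versus 2 doses and no comparator or window for the 54.6%. Neither model lets protection in the 2-dose group wane, which also affects the relative measure.

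**Conclusion.** The point holds on the window. The test-negative estimate covers days 14-28, the main estimate covers 75 days, and no main 3- versus 2-dose estimate exists for the shorter window. The comparison therefore cannot by itself inform on testing-related selection. The gap without any testing bias is about 4 to 16 points under the simple waning paths. In the second model it is about 6 to 27 points with waning, and 0.6 to 6.3 points without. All these figures rest on assumed waning and, in the second model, assumed baseline risk. The direction needs only that 3- versus 2-dose effectiveness falls after day 28.

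The primary estimates are unaffected. This is an additional quality control, subject to national feasibility, and the remedy is a low-cost improvement. The prior-infection issue is a matter of clarity, and the interval rule is not a defect.

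The two endpoint scopes for the 2-dose versus unvaccinated check are a separate, real inconsistency. Nothing in the protocol shows which was intended.

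**What to change.** 1. In section 9.7 or 9.8, add the matched-cohort 3- versus 2-dose infection estimate for days 14-28 after the index date, read from the Kaplan-Meier curves already planned. Name it as the benchmark for the test-negative result. Optionally, restrict it to pairs meeting the 6- or 4.5-month rule.
2. Keep the test-negative interval rule as it is.
3. State in section 9.8 that the no-prior-positive criterion of section 9.2 applies to the test-negative set.
4. Amend the interpretive sentence to say that a comparison with the 75-day result also reflects waning and the different effect measure.
5. Reconcile the two statements in section 9.8 on the endpoints of the 2-dose versus unvaccinated check.

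Item 1 needs one more reading of existing curves, with its bootstrap interval, per comparison and country. Items 2 to 4 are wording, plus one eligibility filter if it was not already intended. Item 5 is wording if the scope is infection only; if it is all endpoints, it adds three analyses (hospitalization, ICU, death). No new data are needed.
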